10.3 Reporting of Serious Adverse Events and Unanticipated Problems

When an adverse event has been identified, the study team will take appropriated action necessary to protect the study participant and then complete the Study Adverse Event Worksheet and log. The sponsor-investigator will evaluate the event and determine the necessary follow-up and reporting required.

- a. Serious Adverse Events will be reported as part of regular adverse event reporting mechanisms via the data capture system and logged for review reporting.

10.31 Investigator Reporting: Notifying the Mayo IRB:

The IRB requirements reflect the guidance documents released by the Office of Human Research Protections (OHRP), and the Food and Drug Administration (FDA) in early 2007 and are respectively entitled “Guidance on Reviewing and Reporting Unanticipated Problems Involving Risks to Subjects or Others and Adverse Events” and “Guidance for Clinical Investigators, Sponsors, and IRBs: Adverse Event Reporting – Improving Human Subject Protection.”

10.311 According to Mayo IRB Policy any serious adverse event (SAE) which the Principal Investigator has determined to be a UPIRTSO must be reported to the Mayo IRB as soon as possible but no later than 5 working days after the investigator first learns of the problem/event.

10.312 Non-UPIRTSO – the investigator reports problems or events that do NOT meet criteria of an UPIRTSO in summary format at the

time of the next continuing review. The investigator monitors the severity and frequency of subsequent non-UPIRTSOs.

Consider the following information to collect when developing any forms for documentation of adverse events.

Example

Information collected on the adverse event worksheet (and entered in the research database):

- Subject's name:
- Medical record number:
- Disease/histology (if applicable):
- The date the adverse event occurred:
- Description of the adverse event:
- Relationship of the adverse event to the research (drug, procedure, or intervention):
- If the adverse event was expected:
- The severity of the adverse event: (use a table to define severity scale 1-5)
- If any intervention was necessary:
- Resolution: (was the incident resolved spontaneously, or after discontinuing treatment)
- Date of Resolution:

The investigator will review all adverse event reports to determine if specific reports need to be made to the IRB and FDA. The investigator will sign and date the adverse event report when it is reviewed. For this protocol, only directly related SAEs/UPIRTSOs will be reported to the IRB.

10.4 Adverse events to be graded at each evaluation and pretreatment symptoms/conditions to be evaluated at baseline per the CTCAE v5.0 grading unless otherwise stated in the table below. Version 4 is allowed if v5 is not available, however, AEs will have to be updated to V5 once is available:

System (SOC)	Organ Class	Adverse event/Symptoms	Baseline	Each evaluation	Grading scale (if not CTCAE)
General		Pain	X	X	CTCAE
Skin and subcutaneous tissue disorders		Dermatitis Radiation	X	X	CTCAE
		Skin hyperpigmentation	X	X	CTCAE
		Skin hypopigmentation	X	X	CTCAE
		Superficial Soft Tissue Fibrosis	X	X	CTCAE
		Breast edema (lymphedema)	X	X	CTCAE

Vascular	Lympedema -arms	X	X	CTCAE
Respiratory, thoracic and mediastinal disorders	Pneumonitis	X	X	CTCAE

10.5 Submit via appropriate *reporting mechanisms* the following AEs experienced by a patient and not specified in Section 10.4:

- 10.52 Grade 3, 4, and 5 AEs regardless of attribution to the study treatment or procedure.
- 10.53 Grade 5 AEs (Death)
- 10.531 Any death within 30 days of the patient's last study treatment or procedure regardless of attribution to the study treatment or procedure
- 10.532 Any death more than 30 days after the patients last study treatment or procedure that is felt to be at least possibly treatment related must also be submitted as a Grade 5 AE, with a CTCAE type and attribution assigned.

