1.3 Rationale for Hypofractionation in Breast Cancer

Hypofractionated, or shorter course, radiotherapy presents an opportunity to enhance access to care, increase convenience and acceptability of therapy, while reducing cost and potentially improving toxicity. Although the use of proton therapy for breast cancer is still in early development, concerns regarding proton therapy have primarily been related to costs, rather than technical feasibility in the clinic. Proton therapy departments are more expensive to build as they require huge accelerators to deliver the beam. While proton therapy is considered more expensive than conventional forms of radiation, cost-benefit studies have suggested cost-effectiveness in the long term due to decreased long term toxicity.³⁶⁻³⁸ An important driver of cost of both photon and proton radiotherapy is the number of treatments delivered to individual patients, with shorter courses resulting in lower expenditures³⁹. Studies are needed to evaluate whether equivalent or improved outcomes can be achieved with shorter courses of therapy.

Furthermore, the optimal dose and fractionation regimen for whole breast irradiation, whole breast and regional nodal irradiation, and postmastectomy radiotherapy remains unknown. While there is widespread clinical experience with standard fractionation, newer preclinical and clinical data support a shorter course of radiotherapy.

For fraction sizes up to approximately 8 Gy, The linear-quadratic formula model is the preferred method of predicting the relationship between fraction size and tissue response of varying radiotherapy regimens. Its origins stem from what has been described as a two-component survival curve for mammalian cells represented by the curvilinear dose-response curve for the log of cell survival.⁴⁰ In it, the biologically effective dose (BED) of a given fractionation regimen is related to the α/β ratio in the following equation, where α represents the \log_e of the cells killed per gray and β is the \log_e of the cells killed per gray squared:

$$\text{BED} = nd(1 + d/\alpha/\beta)$$

d = dose per fraction
 n = # of identical fractions

The ratio of α/β is the dose at which the linear and quadratic components of cell killing are the same. In general, early-responding tissues such as skin desquamation have a high ratio whereas late-responding tissues such as dermal contraction have a low ratio and are very sensitive to increases in fraction size.⁴¹

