Emerging evidence suggests that the α/β ratio of breast cancer may be low and more in line with that of late responding tissues and therefore breast cancer patients may not benefit from prolonged fractionation regimens.^{42,43} Indeed, the most robust data to date suggesting this relationship has come from the UK Standardization of Breast Radiotherapy (START) trials, two modern breast cancer randomized controlled trials examining various fractionation regimens that have recently been reported with 10-year follow-up. In START-A, a regimen of 50Gy in 25 fractions to the whole breast over 5 weeks was compared with 41.6Gy or 39 Gy in 13 fractions over 5 weeks. There was no significant difference in local-regional relapse between the 41.6Gy and 50Gy regimens (6.3% vs 7.4%, p=0.65) or the 39Gy and 50Gy regimens (8.8 vs 7.4%, p=0.41).²⁴ Moderate or marked breast induration, telangiectasia, and breast edema was less common in the 39Gy group compared with the 50Gy group, and rates of these toxicities were no different between the 41.6Gy and 50Gy groups. The treatments in each arm were given over the same time period, enabling an estimate of sensitivity of breast cancer to changes

in fraction size that was not confounded by differences in treatment time. An α/β ratio for local-regional relapse of breast cancer was determined from a meta-analysis of START-A and the START pilot trial (349 events, 3646 women) as 3.5 Gy (95% CI 1.2-5.7). The α/β ratio for normal tissue toxicity endpoints included 3.5Gy (95% CI 0.7-6.4) for breast shrinkage, 4Gy (2.3-5.6) for breast induration, 3.8Gy (1.8-5.7) for telangiectasia, and 4.7 Gy (2.4-7.0) for breast edema, suggesting that normal tissue toxicity may not be reduced and may even be increased when breast cancer radiotherapy fractionation regimens are prolonged with small daily fractions.

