Further evidence supporting hypofractionated regimens for breast cancer came from the START-B clinical trial, in which 50Gy in 25 fractions over 5 weeks was compared with 40Gy in 15 fractions over 3 weeks. There was no difference in local-regional relapse at 10 years between 40Gy and 50Gy groups, (4.3% vs 5.5%, $p=0.2$) but breast shrinkage, telangiectasia, and breast edema were significantly less common with the shorter fractionation regimen. These data are consistent with the results of the Canadian hypofractionation trial which compared 42.5Gy in 16 fractions in 3.2 weeks to 50Gy in 25 fractions over 5 weeks and suggest that the use of smaller fractions is of no benefit in terms of tumor control or reduction in toxicity, at least in the doses used in these studies, and may potentially be deleterious.^{24,44} Interestingly, if one applies an α/β ratio for both normal tissue toxicity and tumor control of 3.5 from START-A, the 40Gy regimen from START-B is equivalent to 44.9Gy in 2 Gy fractions. This may imply that differences in overall treatment time of a course of radiation therapy may be more important than originally thought, potentially allowing further dose reduction when fractionation regimens are shortened, as we propose here.^{45,46}

Other moderate hypofractionated radiotherapy treatments support excellent local control and comparable toxicity outcomes. Ahlawat et al, reported on 83 women treated after breast conserving surgery 36.63 Gy in 11 fractions of 3.33 Gy per day, with a 4 fraction boost of an addition 3.33 Gy⁴⁷. Three year local recurrence free survival was 95.9%, and breast cosmesis was good or excellent in 94% of evaluable patients.

In the FAST trial, 915 women aged ≥ 50 years with node negative early breast cancer after wide local excision were randomly assigned to receive 50 Gy in 25 fractions of 2.0 Gy over 5 weeks versus 28.5 Gy or 30Gy in 5 fractions once weekly fractions of 5.7 Gy or 6.0 Gy. Three-year rates of physician-assessed moderate/marked adverse effects in the breast were 17.3% (13.3-22.3%, $p<0.001$) for 30Gy and 11.1% (7.9-15.6%, $p=0.18$) for 28.5Gy compared with 9.5% (6.5-13.7%) after 50Gy.⁴⁸ Further follow-up is needed to determine local control of these three regimens but promisingly at a median follow-up of 37.3 months in survivors, only 2 ipsilateral breast recurrences were noted.

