2.88 (0.75–5.01) Gy; $a = 0.08 \pm 0.02 \text{ Gy}^{-1}$; potential doubling time $T_d = 14.4 \pm 7.8$ day.⁴³ The fractionation regimens in table 1 (modified from Qi et al.)⁴³ is based on the fitting of clinical data including the hypofractionated randomized trials mentioned above and justifies the five fraction regimen proposed for arm 2. The concurrent boost dose of 6 Gy x 5 is also based in part on the work of Formenti et al. who recently reported the 5-year results of a prospective trial of 3D-CRT APBI of 100 patients treated in the prone position to a total dose of 30Gy in 6Gy fractions. At a median follow-up of 64 months, there has been just one local recurrence and one contralateral recurrence and cosmesis was rated as good/excellent in 89% of patients with at least 36 months follow-up.⁵³ Livi et al has also shown excellent 5-year toxicity, cosmetic outcome and local failure results employing a dose of 30Gy in 5 treatments.⁵⁴ The control arm for this study will be 15 fractions based on the favorable long term follow-up of the UK START B⁵⁵. More recently the initial toxicity results of the fast forward trial have been published. Very low rates of grade 3 toxicity were seen using either the 40 Gy over 3 weeks, or 26 Gy or 27 Gy over one week.⁵⁶ It is possible that the spot proton RBE may be different than 1.1 for hypo-fractionated treatments. Trials like the currently proposed would be critical to define differences in RBE with spot scanned hypofractionated radiation as well as the cancer and normal tissue alpha/beta.

Table 1

Arms	Tx	Tumor dose 2Gy
50Gy in 2Gy	25	50Gy
45Gy in 2.26Gy	20	50Gy
33.4Gy in 3.34Gy	10	50Gy
24.7Gy in 4.98Gy	5	50Gy

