10.22 Assessment of Attribution

Only G4 or G5 adverse events will require an attribution. Any change in the grade of an adverse event within the list of monitored AEs will be recorded and considered to be related to treatment. Any new adverse not listed occurring within the Radiated area or in close proximity will be graded and attribution defined by the study PI.

Events determined to be possibly, probably or definitely attributed to a medical treatment suggest there is evidence to indicate a causal relationship between the treatment and the adverse event.

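### Telangiectasia and breast shrinkage have no solicited row in Section 10.4, so their grade 1-2 late toxicity reaches the arm comparison only through unsolicited reporting

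*Combined protocol and SAP*

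**What the plan says.** **Why fraction size matters here.** Section 1.3 gives alpha/beta estimates of "3.5Gy (95% CI 0.7-6.4) for breast shrinkage, 4Gy (2.3-5.6) for breast induration, 3.8Gy (1.8-5.7) for telangiectasia, and 4.7 Gy (2.4-7.0) for breast edema", and explains that "late-responding tissues such as dermal contraction have a low ratio and are very sensitive to increases in fraction size". It reports from the cited 15- versus 25-fraction trial that "breast shrinkage, telangiectasia, and breast edema were significantly less common with the shorter fractionation regimen". From the cited 13- versus 25-fraction trial it reports less induration, telangiectasia and edema with 39 Gy than with 50 Gy.

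**What is compared.** Late toxicity is a secondary objective (2.21). Section 16.622 takes each woman's maximum grade for each type of late event, from 90 days to 5 years, and compares the arms by chi-squared test. Events that persist past 90 days count, as well as new ones.

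**What is solicited.** Section 10.4 lists eight terms for grading at baseline and each evaluation: pain, radiation dermatitis, hyperpigmentation, hypopigmentation, "Superficial Soft Tissue Fibrosis", breast edema, arm lymphedema and pneumonitis.

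**What happens to unlisted events.** Section 10.5 asks for submission of "the following AEs experienced by a patient and not specified in Section 10.4" and then names grades 3, 4 and 5. Section 10.22 is wider: "Any new adverse not listed occurring within the Radiated area or in close proximity will be graded", with no minimum grade, and the study PI defines attribution. Section 18.1 provides a form called Adverse Events: Other, completed when applicable.

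**The concern.** The trial's question is whether 5 fractions harm the breast more than 15. The protocol itself picks out four late effects by their fraction-size response, yet two of them are not on the list that prompts the clinician at each visit.

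Two things follow for the low grades. A blank cannot be read as absent, because nobody was asked to look. And there is no baseline grade to set a later finding against, which matters most for shrinkage: every participant has had breast-conserving surgery before randomisation, so a size difference may already be present.

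Unsolicited capture also leaves room for arm-dependent reporting. If p is the true rate in an arm and c the chance that an event is written down, the recorded rate is c × p. With equal c in both arms, the recorded difference shrinks by the factor c. With unequal c, equal true rates give a spurious difference of p × (c₂ − c₁). Clinic staff know the arm, so equal c cannot be taken for granted.

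**Working it through.** **1. Coverage of the four named effects.**

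| Effect (1.3) | Row in 10.4 | Other systematic capture |
|---|---|---|
| Induration | Superficial soft tissue fibrosis (approximate match) | Cosmesis scale; patient texture item |
| Edema | Breast edema | Patient swelling item |
| Shrinkage | None | Cosmesis scale (size and shape, global grade); patient breast-size and shape items |
| Telangiectasia | None | Patient spider-vein item, 0 to 10 |

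Two of four have a solicited row. Matching induration to fibrosis is a judgement; without it, one of four has an exact term.

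**2. Coverage of the effects that differed in the cited trials.** In the 15- versus 25-fraction trial the three were shrinkage, telangiectasia and edema: one of three is solicited. In the 13- versus 25-fraction trial they were induration, telangiectasia and edema: two of three. Telangiectasia is in both sets and is solicited in neither case.

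**3. The two rules for unlisted events.** Take a new grade 2 telangiectasia in the treated breast. Under 10.22 it will be graded. Under 10.5 it need not be submitted. The plan does not say which rule decides whether it reaches the 16.622 table. Neither rule prompts for it or asks for a baseline grade.

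**4. Are these two effects the ones most likely to differ?** The four alpha/beta intervals are 0.7-6.4, 2.3-5.6, 1.8-5.7 and 2.4-7.0 Gy. They share the range 2.4-5.6 Gy, and all four point estimates (3.5, 4, 3.8, 4.7) lie inside it.

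The linear-quadratic formula of 1.3 gives the same answer. The dose in 2 Gy fractions is D × (d + α/β)/(2 + α/β). It reproduces the protocol's own figure: 40 × (2.67 + 3.5)/5.5 = 44.87, stated as 44.9 Gy. For the whole-breast doses in 7.3, without boost:

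| Effect | α/β | 40.05 Gy in 15 | 25 Gy in 5 | Difference |
|---|---|---|---|---|
| Shrinkage | 3.5 | 44.93 | 38.64 | 6.29 |
| Telangiectasia | 3.8 | 44.68 | 37.93 | 6.75 |
| Induration | 4.0 | 44.52 | 37.50 | 7.02 |
| Edema | 4.7 | 44.05 | 36.19 | 7.86 |

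This ignores overall treatment time and any change in RBE, and serves only to rank the effects. The two unsolicited effects do not come out with the largest contrast.

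**5. Does the primary analysis depend on the list?** The sample size uses only the composite complication rate: (1.645 + 0.842)² × (0.10 × 0.90 + 0.10 × 0.90)/0.15² = 49.5, so 50 per arm, as Section 16.4 states. Grade 3 or higher events are submitted under 10.5 whether listed or not. Adding rows changes neither.

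**The case against.** The best defence is that the plan already sees these effects by other routes. Section 10.22 promises a grade for any new unlisted event in the field, and 18.1 has a form for it. Trained nurses score cosmesis on a scale whose anchors refer to size and shape. A panel blinded to allocation rates photographs from baseline and 2 years (16.3, 16.632). Patients report spider veins, breast size and breast shape, and 16.631 compares patient measures between arms with mixed models.

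Much of this stands. A reader might infer that the arms are compared with no clinician grades at all for these effects; 10.22 and 10.5 rule that out. Shrinkage is not invisible either, since it feeds a clinician-scored part of the primary endpoint.

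What does not stand is that these routes replace a solicited grade. Cosmesis and the panel give one global rating from which shrinkage cannot be separated, and the scale's wording does not name telangiectasia. Cosmesis is not required at outside visits (4.0, footnote 13), although footnote 12 shows that new rows could be missed there too. Footnote 3 leaves photograph timing to the physician. The patient items are exploratory and are not CTCAE grades. The form for other events is completed when applicable, so it depends on someone raising the event.

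It is also fair to say that no rate or detectable difference can be attached to the gap. The documents give no low-grade rates for these effects.

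**Conclusion.** The point holds as a limited gap in a secondary comparison. Two of the four late effects with a quoted alpha/beta value have no solicited CTCAE row, so their grade 1-2 late toxicity enters 16.622 only through unsolicited, open-label reporting without a baseline grade. Telangiectasia is the stronger half. The count rests on reading superficial soft tissue fibrosis as induration.

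Three further inferences are tempting and are not supported:

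- That these are the effects most likely to differ between 5 and 15 fractions. The quoted intervals overlap too much to rank them, and the protocol's own model does not put them first.
- That the trial fails a goal of estimating normal-tissue sensitivity. Section 1.4 says that trials like this one would help define RBE differences "as well as the cancer and normal tissue alpha/beta", but this is rationale; no objective in Section 2 and no analysis in Section 16 estimates it.
- That severe events are missed in the primary endpoint. Section 10.5 covers grade 3 and above regardless of the list.

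This is a cheap improvement worth making. It does not challenge the trial's main conclusion.

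**What to change.** Add two rows, telangiectasia and breast shrinkage/atrophy, to the 10.4 table and the Adverse Events Solicited form. Grade both on CTCAE at baseline and each evaluation, and analyse them under 16.622 like the other listed terms.

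Reconcile 10.22 with 10.5, stating whether an unlisted event in or near the field below grade 3 must be recorded and submitted, and whether it enters 16.622.

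For women already enrolled, start at the next visit and report that their baseline grade is missing. Visits already completed cannot be recovered, but follow-up to 5 years leaves any remaining visits usable.

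The cost is two more lines on an existing form per visit, and incomplete baseline data for women already enrolled. No new visit, assessor or procedure is needed.

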11.0 Treatment Evaluation

- 11.1 Patients will be evaluated at baseline, then according to the Assessment Schedule (Section 4.0)
- 11.2 At the time of reevaluation, patients will be classified in the following manner:
 - 11.2.1 No evidence of disease (NED).
 - 11.2.2 Recurrence of disease (REC). Consider biopsy of the site and PET scan.
 - 11.2.3 The site of recurrence (or failure) will also be collected and classified as local vs. regional vs. distant recurrence.
 - 11.2.4 Secondary Treatment. The date of the first retreatment and extent of retreatment post-recurrence (i.e. secondary resection or re-irradiation for primary disease), will be collected. Pathology, if available, and operative reports are required to be submitted per Section 18.0.
- 11.3 Cosmesis evaluation and Patient Reported Outcomes
 - 11.3.1 The Harvard/NSABP/RTOG Cosmesis Scale will be used to score cosmesis by trained nurses for the primary endpoint according to the schedule outlined in section 4.0.

Excellent: Treated breast nearly identical to untreated breast

Good: Treated breast slightly different than untreated (minimal but identifiable effects of the treated breast). Mild reddening or darkening of the breast may be present. Thickening or scar tissue causes only a mild change in the shape or size.

Fair: Obvious difference in the size and shape of the treated breast. **The change involves one-quarter or less of the breast.** Severe thickening or scarring can be present.

Poor: Marked change in appearance or shape involving **more than one-quarter or less of the breast.** Treated breast seriously distorted (severe sequelae of breast tissue)

11.3.2 Digital photographs should be performed according to the schedule outlined in section 4.0 and should include three poses: from the front with hands on hips, both oblique and lateral views with hands behind the back. Recommended framing should go from the sternal notch to the umbilicus. If possible, patients should be photographed against a solid colored background such as a white sheet.

11.3.3 The Quality of Life (QOL) questionnaires are adapted from the Breast Cancer Treatment Outcome Scale (BCTOS). PRO-CTCAE will also be used for QOL questionnaires.

11.4 Quality of life questionnaires are being done as part of the standard of care for all patients. We will correlate results of this standard of care questionnaires with clinical outcomes.

11.4.1 The Quality of Life (QOL) questionnaires are adapted from the Breast Cancer Treatment Outcome Scale (BCTOS). PRO-CTCAE will also be used for QOL questionnaires.

Unplanned surgical intervention will be adjudicated by a plastic surgeon and a general surgeon.

